5.7 Visit Schedule

The design and number of visits mirror the standard of care pathway for patients undergoing either focal therapy or radical therapy, so that additional patient burden is minimal. Prior to enrolment, all patients will have undergone a Prostate Specific Antigen (PSA) blood test, a diagnostic prostate MRI and prostate biopsies. A standard of care (SOC) multi-disciplinary team case review will precede any discussion with the patient on all suitable treatment options and trial suitability. After an MDT discussion confirming suitability for FT and/or radical therapy has taken place, a patient information sheet (PIS) explaining the study will be provided, after which patients will be given a minimum of 24 hours to consider taking part. We aim for consent to be taken during a SOC appointment, or an additional consultation via phone, or in person. Randomisation will take place during the visit in which consent is taken along with any required neoadjuvant therapy, as allocated via randomisation, to be prescribed and within 24 hours of receiving the prescription. Time from randomisation will be used to define progression free survival and failure free survival. The end of treatment is defined as the final part of any intervention. For radiotherapy, this is the final radiation fraction completed and for prostatectomy and focal therapy the point at which the catheter is removed. Therefore, the follow-up visits noted below will start from these time-points, which will define the date of first follow-up visit (visit 2).

Protocol No: 19CX5006 v5.0 13th July 2022

IP4 - CHRONOS 19CX5006 Imperial College London Date: 13 th July 2022

Visit Schedule:

	Screening & Consent	Visit						
Visit	1	2	3	4	5	6	7	6 monthly visits until last visit 60 months after visit 2
Months		These below specify the months after the completion of each treatment in each arm						
		0	3	12	18	24	30	31-60. Visits 4 onwards can be telephone consultations in order t note clinical outcomes although MRI scans and biopsies where done will require physical visits to the hospital
Informed Consent and enrolment into either CHRONOS A or CHRONOS B	Х							
Inclusion & exclusion criteria checked, including concomitant medication review	Х							
Randomisation	Х							
Prescription of neo- adjuvant therapy	X (if randomised to such arm)							Within 24hrs of randomisation
PSA blood test	Such anny		Х	Х	Х	Х	Х	X (6 monthly)
Prostate Contrast MRI	X (if randomised to focal therapy and no contrast given during diagnostic scan – to have prior to visit 2)							
Prostate mpMRI				X (focal therapy arms)				
Biopsy (optional)				X (focal therapy arms)				
Treatment		X (these vary in length)		,				X (focal therapy arms – a second treatment will be permitted for a histologically confirmed recurrent residual or new out-of-field disease)
Clinical assessment (optional, only if required)			X	Х	X	X	X	
PROMS questionnaires	Х		Х	Х		Х		X (every 12 months, at 24, 36, 48 and 60 months visits)
Review/ reporting of patient AEs/SAEs		X	Х	Х	X	X	Х	X
Blood and urine tests including those for	Х		Х	Х				Х

Short Title:	Protocol No:	Sponsor:	Version: 5.0
IP4 - CHRONOS	19CX5006	Imperial College London	Date:
			13 th July 2022

biobanking (optional)				

Time window for each visit will be +/- 4 weeks

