5.3 Randomisation

Randomisation will take place centrally via the InForm system. Randomisation will be blocked and stratified by the following stratification factors:

- Tumour grade (Gleason 6 [grade group 1], Gleason 7 [grade group 2], Gleason 7 [grade group 3])

Short Title: Protocol No: Sponsor: Version: 5.0 Date: 13 th July 2022	
--	--

- Local stage (T2 versus radiological (MRI) T3)

CHRONOS-A only: Previous or current 5ARI use

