Planned interim analyses for education: there will be a review of recruitment into each research arm and these results as well as the qualitative outcomes will be used for submission for a research doctoral thesis of [name] supervised by the Chief Investigator of this trial. The thesis will be embargoed to public release as deemed necessary by the TSC/DMC.

CHRONOS-B: Interim monitoring and analyses: For each research comparison one formal intermediate analysis is planned, where an activity "hurdle" is determined on the intermediate primary outcome measure, FFS. Each research arm needs to pass this in order to continue recruitment. This will initially be timed according to the observed number of interim events required for a formal interim analysis (Table 2).

Table 2: Guidelines for stopping accrual and trigger for analysis

Stage	Arm Ratio	Target HR	One-sided alpha	Power	HR cut-point	Control arm events
2 Activity	1:1	0.67	0.45	95%	>0.974	~47FFS
3 Efficacy	1:1	0.67	0.025	85%	-	~120FFS
Overall	-	-	0.044	83%	-	-

For each comparison that continues recruitment into its final efficacy stage, the final analysis will be triggered by a pre-specified number of definitive primary outcome events being reported for the relevant patients on the control arm of that comparison (Table 2).

Further details of the planned analysis of the secondary outcomes and methods for dealing with missing data will be given in the Statistical Analysis Plan. Any deviation from the statistical analysis plan will be described and the reason for the deviation explained.

i. Primary Outcome Measure Analysis

The primary endpoint (PFS or FFS) analysis consists of a Cox proportional hazard model to investigate the effect of the intervention on PFS/FFS adjusted by the stratification variables.

The assumption of proportional-hazards (PH) will be tested and appropriate methods applied to the data in the case of any violation. If there is no evidence of non-PH in the treatment effect, the HR for the adjusted Cox model takes primacy. If there is evidence of non-proportional hazards in the treatment effect, the HRs are difficult to interpret and the

Short Title:	Protocol No:	Sponsor:	Version: 5.0
IP4 - CHRONOS	19CX5006	Imperial College London	Date:
			13 th July 2022

restricted mean survival time (RMST) constructed from a flexible parametric model with time varying treatment effects will take primacy.

ii. Secondary Outcome Measure Analysis

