Details of the secondary endpoints analysis will be outlined in the Statistical Analysis Plan document, which will be written and signed off before any analysis will commence.

iii.Adjusted analysis

Analysis will be adjusted by the pre-specified stratification variables

iv.Safety Analysis

Safety analysis consists in tabulating the frequency of serious adverse events.

Short Title: IP4 - CHRONOS	Protocol No: 19CX5006	Sponsor: Imperial College London	Version: 5.0 Date: 13 th July 2022
			10 daily 2022

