6.7.2. Visit Schedule

The design and number of visits mirror the standard of care pathway for patients undergoing either focal therapy or radical therapy, so that additional patient burden is minimal. Prior to enrolment, all patients will have undergone a Prostate Specific Antigen (PSA) blood test, a diagnostic prostate MRI and prostate biopsies. A standard of care (SOC) multi-disciplinary team case review will precede any discussion with the patient on all suitable treatment options and trial suitability. After an MDT discussion confirming suitability for FT and/or radical therapy has taken place, a patient information sheet (PIS) explaining the study will be provided, after which patients will be given a minimum of 24 hours to consider taking part. We aim for consent to be taken during a SOC appointment, or an additional consultation via phone, or in person. Randomisation will take place during the visit in which consent is taken along with any required neoadjuvant therapy, as allocated via randomisation, to be prescribed and within 24 hours of receiving the prescription. Time from randomisation will be used to define progression free survival and failure free survival. The end of treatment is defined as the final part of any intervention. For radiotherapy, this is the final radiation fraction completed and for prostatectomy and focal therapy the point at which the catheter is removed. Therefore, the follow-up visits noted below will start from these time-points, which will define the date of first follow-up visit (visit 2).

	Screening & Consent	Visit						
Visit	1	2	3	4	5	6	7	6 monthly visits until last visit 60 months after visit 2
Months				se below spec ach arm	ify the	e mon	ths af	ter the completion of each treatment
		0	3	12	18	24	30	31-60. Visits 4 onwards can be telephone consultations in order to note clinical outcomes although MRI scans and biopsies where done will require physical visits to the hospital
Informed Consent and enrolment into either CHRONOS A or CHRONOS B	Х							
Inclusion & exclusion criteria checked, including concomitant medication review	х							
Randomisation	x							
Prescription of neo- adjuvant therapy	X (if randomised to such arm)							Within 24hrs of randomisation
PSA blood test			Х	Х	Х	Х	Х	X (6 monthly)
Prostate Contrast MRI	X (if randomised to focal therapy and no contrast given during diagnostic scan – to have prior to visit 2)							
Prostate mpMRI				X (focal therapy arms)				

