8.1. Baseline Demographic Variables

After obtaining informed consent and registering the patient in one of the studies (CHRONOS-A or CHRONOS-B), the following clinical and baseline assessments will be undertaken:

- Demographics: age, ethnicity, IMD decile
- Digital Rectal Examination results
- Details of current medications
- IPSS score
- MCCL and Gleason grade at pre-enrolment biopsy.

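### PSA is known for every man before enrolment but is neither a listed baseline variable nor a covariate in the PFS/FFS model, which forgoes a little power in CHRONOS-B

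*Protocol*

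**What the plan says.** **Availability.** Protocol section 5.7: "Prior to enrolment, all patients will have undergone a Prostate Specific Antigen (PSA) blood test, a diagnostic prostate MRI and prostate biopsies". Section 4.1 makes a PSA of at most 20 ng/ml an inclusion criterion. In the visit schedules of both documents the PSA row is first marked at Visit 3, three months after treatment.

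**Baseline reporting.** The list in SAP section 8.1 opens with "Demographics: age, ethnicity, IMD decile", goes on to rectal examination, medications and IPSS, and closes with "MCCL and Gleason grade at pre-enrolment biopsy". PSA is not in it, nor in Tables 1.1 and 1.5. PSA appears in the SAP tables only as a reason for ineligibility (Table 2.11).

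**Model.** Protocol section 8.3(i) uses a Cox model to "investigate the effect of the intervention on PFS/FFS adjusted by the stratification variables", and 8.3(iii) adds: "Analysis will be adjusted by the pre-specified stratification variables". By section 5.3 these variables are tumour grade and local stage in both trials, and 5ARI use in CHRONOS-A only. The FFS model of CHRONOS-B therefore carries grade and stage alone. If hazards are not proportional, RMST from a flexible parametric model takes over, and no further covariates are named for it.

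**The concern.** PSA, grade and stage all bear on entry. Grade and stage are used to stratify and to adjust. PSA, equally available and on a continuous scale, is used for neither. In a Cox model, omitting a prognostic covariate pulls the estimated treatment hazard ratio towards 1, even under perfect randomisation. In a superiority comparison such as CHRONOS-B that costs power. Without PSA in the baseline tables, a reader also cannot see whether the arms were alike on it, which is most likely to be noticed in the pilot with 30 or 20 men per arm.

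The model covariates are fixed in the protocol. Section 8.3 leaves secondary outcomes and missing-data methods to the SAP, but not the covariates of the primary model.

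**Working it through.** **1. Reproduce the plan's figure (CHRONOS-B).** Inputs from Protocol section 8.1.2 and Tables 1 and 2: HR 0.67, one-sided alpha 0.025, power 85%, control failure 20% at 3 years and 30% at 5 years, 400 per arm.

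- Ratio of treated to control events under exponential FFS: r = (1 − 0.8^0.67)/0.2 = 0.694, or (1 − 0.7^0.67)/0.3 = 0.709.
- Control events = [1.960·√2 + 1.036·√(1 + 1/r)]² / (ln 0.67)² = 120.2 or 119.7. Stated: 120.
- Stage 1 (alpha 0.45, power 95%): 47.1 or 46.5, stated 47. Critical HR = exp(−0.1257·√(2/47)) = 0.974, as stated.

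**2. Why the simulations below start near 81% rather than 85%.** The plan's formula sets the critical value with the null SE √(2/120) = 0.129, giving Φ[(0.4005 − 1.96×0.1291)/0.1418] = Φ(1.04) = 85%. A Wald test uses the SE with about 85 treated-arm events, √(1/120 + 1/85) = 0.142, giving Φ(0.4005/0.1418 − 1.96) = Φ(0.865) = 81%. The gap is one of method and has nothing to do with PSA.

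**3. Effect of adding PSA in CHRONOS-B.** The prognostic strength of PSA is an **assumption**, shown as a range of HR per SD of log PSA, to be read as its effect given grade and stage. One comparison, 400 v 400, HR 0.67 conditional on PSA, 30% control failure at 5 years, one-sided 2.5% Wald test, power in %:

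| Assumed HR per SD | Follow-up 2.6–7.6 y, 5,000 replicates: without → with | Follow-up 2.6–7.6 y, 1,500 replicates: without → with |
|---|---|---|
| 1.2 | 81.1 → 81.5 (+0.4) | 80.5 → 80.9 (+0.4) |
| 1.4 | 79.8 → 81.1 (+1.3) | 79.6 → 81.1 (+1.5) |
| 1.6 | 79.3 → 81.9 (+2.6) | 78.2 → 81.2 (+3.0) |
| 1.8 | 78.6 → 82.7 (+4.1) | 78.7 → 81.9 (+3.2) |
| 2.0 | not run | 75.3 → 81.1 (+5.8) |

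With every man censored at 5 years instead (1,500 replicates, Monte Carlo error about 1 point):

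| Assumed HR per SD | Power without → with | Mean HR without → with | SE of log HR without → with |
|---|---|---|---|
| 1.00 | 82.5 → 82.3 | 0.665 → 0.665 | 0.1423 → 0.1424 |
| 1.22 | 80.6 → 81.1 | 0.670 → 0.668 | 0.1422 → 0.1423 |
| 1.49 | 78.6 → 80.2 | 0.677 → 0.671 | 0.1419 → 0.1420 |
| 2.01 | 75.9 → 81.7 | 0.688 → 0.668 | 0.1413 → 0.1416 |

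The gain comes from less attenuation of the HR. The SE does not fall.

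**4. CHRONOS-A.** 1190 × 0.95 ≈ 1130 evaluable men, about 136 events, true HR 1, one-sided 5% (the protocol does not state sidedness). Margin as HR: ln 0.80/ln 0.85 = 1.373 from the stated 0.85 and 0.05, and also ln 0.85/ln 0.90 = 1.542, which is the value that returns the stated 136 events. That discrepancy is a separate matter. The mean SE is 0.173 with and without PSA in every setting. Across both margins and all assumed strengths, non-inferiority power changes by at most 1.0 point (largest change 83.5% → 82.5%).

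**5. Chance imbalance.** The SD of the between-arm difference, in SD units of log PSA, is √(2/n): 0.058 at 595 per arm, 0.071 at 400, 0.26 at 30 and 0.32 at 20. For an assumed log HR per SD of 0.2 to 0.7, a one-SD imbalance multiplies the HR by exp(0.2×0.058) = 1.012 to exp(0.7×0.058) = 1.041 in CHRONOS-A, and by 1.014 to 1.051 in CHRONOS-B. The SE of the log HR is about 0.17 and 0.14 respectively.

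**The case against.** The case for leaving the plan alone is substantial.

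- **The planned analysis is valid.** Adjusting for the stratification factors is pre-specified and sound. This stands.
- **The loss depends on definition.** The protocol powers on HR 0.67 without PSA. If 0.67 is the effect without PSA adjustment, nothing is lost against plan and adjustment is a bonus. This also stands, so the result is best described as power available but not used.
- **The size is assumed.** The simulations contain no grade or stage, and PSA is capped at 20 ng/ml, so the low end of the range may apply. There the gain is close to simulation error.
- **The SAP covers feasibility only.** It has no PFS/FFS analysis for PSA to affect, the main stage depends on funding, and no main-stage SAP is among the documents. That limits the weight of the missing table rows. It does not touch the model, which the protocol fixes.

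A reader might go further than the documents allow in four ways.

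- **That PSA is not collected at baseline.** The blank screening cell does not show this. The diagnostic biopsy has no screening mark either, yet its Gleason grade and core length are baseline variables. Eligibility is checked at Visit 1, and the eCRF is not among the documents.
- **That imbalance biases the result.** Under randomisation it has no direction and is already allowed for in the confidence interval.
- **That attenuation makes a false non-inferiority claim materially easier.** With truth placed at HR 1.373 (565 per arm, assumed follow-up 3 to 8 years, one-sided 5%), false claims ran at 5.9, 6.9 and 6.4% without PSA, and 5.4, 5.8 and 5.3% with it, for assumed HRs per SD of 1.4, 1.6 and 2.0 (Monte Carlo error about 0.6 points). The difference is small and requires the margin to be an HR conditional on PSA. Section 8.1.2 sets it as an absolute 0.05 in PFS.
- **That PSA-based failure rules make baseline PSA matter more.** Those rules use post-treatment values only (Protocol section 5.9).

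**Conclusion.** The point holds as a minor improvement in efficiency and reporting. A baseline value already in hand for every man is neither tabulated nor used in the primary model. The power forgone in CHRONOS-B is about 0 to 2 points if the HR per SD of log PSA, given grade and stage, is 1.2 to 1.5, and about 3 to 6 points if it is 1.6 to 2.0. These figures rest on that assumed strength and on reading 0.67 as the HR conditional on PSA. If PSA adds nothing to grade and stage, the gain is nil and the cost of the extra term is negligible (82.5% v 82.3%, within simulation error).

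It would be wrong to conclude that precision is lost in the usual sense, that the treatment comparison is invalid, or that either trial needs a different sample size.

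**What to change.** 1. Make sure the last pre-enrolment PSA value and its date are held on the eCRF. Pilot men are carried into the main stage (Protocol section 8.1.1), so holding it now avoids later retrieval for 60 men per trial.
2. Add PSA to SAP section 8.1 and to Tables 1.1 and 1.5.
3. In the protocol and the main-stage SAP, before outcomes are seen, pre-specify log PSA as a continuous covariate alongside the stratification variables, both in the Cox model and in the flexible parametric model used for RMST. State that the HR is then conditional on PSA.

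The cost is at most one eCRF field, one row in each of two tables and one model term. No extra blood test and no change in patient numbers follow. A covariate chosen after outcomes are known would look data-driven, so timing is the only real constraint.

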2.2 Main Study Primary Objectives

CHRONOS-A

To evaluate progression-free survival (PFS) rates of focal therapy alone compared to radical therapy (radiotherapy or surgery) in the treatment of non-metastatic clinically significant prostate cancer. PFS is defined as time from randomisation to salvage whole-gland or systemic therapy, prostate cancer metastases or prostate cancer-specific mortality.

CHRONOS-B

Short Title: IP4 - CHRONOS	Protocol No: 19CX5006	Sponsor: Imperial College London	Version: 5.0 Date: 13 th July 2022
			-

• To evaluate Failure-Free-Survival (FFS) rates of focal therapy alone compared to focal therapy combined with other therapies as a neoadjuvant strategy. FFS is defined as time from randomisation to further focal therapy session or salvage whole-gland or systemic therapy or prostate cancer metastases or prostate cancer-specific mortality.

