 Arm 1 (Control arm): Focal therapy alone (high intensity focused ultrasound [HIFU] or cryotherapy or other validated energy modality as per physician and centre choice). A second treatment in-field, or a first focal ablation to an out-of-field progressive or de novo lesion will be allowed but will be regarded as failure events for the purpose of CHRONOS-B. Cryotherapy can be used after HIFU and HIFU can be used after

Short Title: IP4 - CHRONOS	Protocol No: 19CX5006	Sponsor: Imperial College London	Version: 5.0 Date: 13 th July 2022
			10 daily 2022

cryotherapy. Where patients have undergone hemiablation to one lobe and then undergo hemiablation of the contralateral lobe will be designated as failure of focal therapy

- Arm 2 (Intervention arm): Neoadjuvant finasteride 5mg once daily for a minimum of 12 weeks (84 days) followed by focal therapy (as per control arm).
- Arm 3 (Intervention arm): Neoadjuvant bicalutamide 50mg once daily therapy for 12 weeks (84 days) followed by focal therapy (as per control arm).

Other arms can be added in future with protocol amendments.

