The patients should complete the quality of life and the resource use data questionnaires independently without discussion with friends or relatives and all questions should be answered. The member of the study team should check each questionnaire and query any missing or incorrect data with the patient. Checks should also take place for date and identifiers. Patients should be approached at appropriate visits to complete the questionnaires.

Follow-up consultations

Short Title: IP4 - CHRONOS	Protocol No: 19CX5006	Sponsor: Imperial College London	Version: 5.0 Date: 13 th July 2022
			-

Collection of data at each time point will be permissible via postal, electronic, telephone or face-to-face communication. Unless the patient requests face-to-face visits they will only require attendance for hospitals visits that are defined by the local hospitals follow-up protocol within standard care. In certain circumstances it may be appropriate to replace hospital visits with telephone or email consultations providing that it is still possible to collect all the necessary follow-up information. In order to maintain confidentiality during email consultations these episodes will be conducted via the local site practitioner's protected NHS email account. Such remote consultations are undertaken frequently in routine clinical care and in these instances, it is acceptable to perform appointments with telephone or email consultations providing the required blood results, such as PSA tests are available to the research team (can be performed at local hospital or GP practice as per patients request and the GP's discretion). In any instance the hospital will carry out these tests if the GP was to refuse. All necessary information required to complete the follow-up case report form (CRF) is still required. All details on the telehealth consultations must be recorded in the patients' notes.

Study Visits - specific tests and definitions of failure

Focal therapy

- A prostate mpMRI and an optional targeted transrectal or transperineal prostate biopsy of the treated area at 12 months after focal therapy in CHRONOS-A and CHRONOS-B. Biopsies of the untreated area should only occur if new areas of score 4 or 5 occur. Those men who did not have a diagnostic quality mpMRI compliant with national guidelines before focal therapy should have biopsies of treated and untreated areas, if this is done. A biopsy SOP will give detail the requirements of the biopsy.

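### CHRONOS-B times failure-free survival from randomisation but times visits from focal therapy, so the 12-week drug lead-in can pass for better ablation unless the plan states its question and adds a common-clock analysis

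*Protocol*

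**What the plan says.** **Outcome clock.** Protocol section 2.2 states that "FFS is defined as time from randomisation to further focal therapy session or salvage whole-gland or systemic therapy" (metastases and prostate cancer death complete the list), and section 5.7 repeats the origin: "Time from randomisation will be used to define progression free survival and failure free survival".

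**Assessment clock.** Section 5.7 defines the end of focal therapy (FT) as catheter removal and continues: "Therefore, the follow-up visits noted below will start from these time-points". The only imaging for failure that the protocol schedules is in section 5.9: an mpMRI with an "optional targeted transrectal or transperineal prostate biopsy of the treated area at 12 months after focal therapy in CHRONOS-A and CHRONOS-B". Later imaging is for cause.

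**Lead-in.** Section 5.8 gives the finasteride arm as "Neoadjuvant finasteride 5mg once daily for a minimum of 12 weeks (84 days) followed by focal therapy". The bicalutamide arm also has 12 weeks of drug before FT. Section 6.4 has the drug prescribed and dispensed within 24 hours of randomisation. Control men have no lead-in, and no target or expected time from randomisation to FT is given for them.

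**Analysis.** Section 8.3 specifies a log-rank test and an adjusted Cox model, with restricted mean survival time (RMST) taking over if hazards are not proportional. It has no offset, common calendar or sensitivity analysis for the lead-in. The SAP covers the feasibility stage only. It summarises days from randomisation to treatment by arm (sections 8.3 and 9.3) but does not use them in an outcome analysis.

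**The concern.** A further FT session cannot precede the first. Section 1.1 expects repeat FT in roughly 20 to 30% of men over about five years, salvage radical or systemic therapy in 10% and metastases in 3%. Most failure-free survival (FFS) events are therefore tied to the date of FT. If drug-arm men reach FT later than controls, those events come later on the randomisation clock by the same amount, whether or not the drug improved the ablation.

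Sections 1.2 and 1.2.1 give the reason for the drugs as better ablation: less heat-sink effect and better cell kill. A delay equal to the lead-in is not evidence of that. An inactive drug could pass the interim hurdle more often than intended, and its benefit could then be reported as improved ablation.

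**Working it through.** **Inputs (Protocol sections 8.1.2 and 8.3).** 400 men per arm; 20 per month over 5 years; 20% of controls failing by 3 years (hazard −ln(0.8)/3 = 0.0744 per year) or 30% by 5 years (−ln(0.7)/5 = 0.0713); interim at 47 control events with HR cut-point 0.974 (one-sided alpha 0.45); final at 120 control events, one-sided alpha 0.025, target HR 0.67. The control wait for FT is **not stated**, so the net delay (drug-arm minus control-arm time to FT) is varied.

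**1. The plan's own figures reproduce.**
- Final: null SE of log HR = √(2/120) = 0.129, so the critical HR is exp(−1.96 × 0.129) = 0.776. With 85.6 expected drug-arm events the SE under the alternative is √(1/120 + 1/85.6) = 0.1415. Power = Φ((0.4005 − 0.2530)/0.1415) = 0.851 (stated 85%).
- Interim: exp(−0.1257 × √(2/47)) = 0.974 (stated 0.974).
- Simulated two-stage power is 0.829 (stated 83%).

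**2. Hand check of a 12-week net delay with no drug effect after FT.** 12 weeks = 12/52.18 = 0.230 years.
- Control failures in a window when no drug-arm failure can occur: 400 × (1 − exp(−0.0744 × 0.230)) ≈ 6.8.
- Drift in the log-rank z: (6.84/2)/√((240 − 6.84)/4) = 3.42/7.63 ≈ 0.45.
- One-sided error: 1 − Φ(1.96 − 0.45) ≈ 0.065. The same formula gives 0.035 at 4 weeks and 0.048 at 8 weeks.

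**3. Simulation of the three-arm, two-stage trial** (12,000 to 15,000 runs per scenario; exponential failure from FT; every man reaches FT; no dropout; the null is that the drug does not change failure measured from FT). One-sided error per comparison at the final test, stated 0.025:

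| Net delay | Failures surface continuously | Failures surface at visits |
|---|---|---|
| 0 weeks | 0.024 | 0.026 |
| 4 weeks | 0.036 | 0.044 |
| 8 weeks | 0.050 | 0.060 |
| 12 weeks | 0.070 | 0.080 |

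The visit version detects failure at 12 months after FT and 6-monthly thereafter, each ±4 weeks.

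**4. Further results at 12 weeks** (continuous / visit-driven where two figures are given).
- Error for either arm: 0.117 / 0.133 (stated overall 0.044).
- Mean HR for an inactive drug: about 0.94 / 0.93.
- Stopping follow-up 5 years after randomisation: 0.069 / 0.078, so this does not help.
- RMST to 5 years, computed from Kaplan–Meier curves as a stand-in for the flexible parametric model: 0.104 / 0.107, so the fallback does not remove it.
- Timing from FT in all arms: 0.023 / 0.027.
- If the true HR is 0.67 (continuous detection), the mean estimate moves to 0.63 and two-stage power rises from 0.829 to 0.910.

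**5. Interim hurdle.** In a separate simulation with continuous detection, an inactive drug passes 0.974 in about 47%, 55%, 63% and 69% of trials at net delays of 0, 4, 8 and 12 weeks.

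**6. Conflicting clocks.** Section 5.9 takes the focal PSA reference value 12 months after randomisation, while the visits supplying it run from FT. Section 5.7 ends visits 60 months after visit 2; section 5.9 ends PSA follow-up 5 years after randomisation. For a drug-arm man those end dates differ by at least the 12-week lead-in.

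**The case against.** A reader might infer that the lead-in delays every failure and that the stated 2.5% error is simply not held. The documents do not support that, for three reasons.

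- **The null.** The written objective is FFS from randomisation, and section 1.4 words the hoped-for benefit as a longer time until repeat FT or salvage treatment. For equality of FFS between randomised strategies, a later failure is a real difference and the test holds its error. Inflation exists only against the null that the drug does not change failure after FT. This stands, and it makes the gap an unstated question, not a broken test.
- **The events.** Systemic therapy, metastases and prostate cancer death need not move with the lead-in, and imaging after the 12-month scan is for cause. This stands, although repeat FT is expected to dominate.
- **The size.** Controls wait too: some need a contrast MRI, some need central review, and some are treated at another site. If waits were equal, 0.025 would hold. This also stands, and is why only a range can be given. Even so, a 4-week difference already gives 0.036 to 0.044.

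Making FT the primary origin would also have a cost. The clock would start after randomisation, at a date that treatment itself affects, and men who never reach FT would drop out of the comparison or need a special rule. That argues against replacing the primary analysis, but not against a sensitivity analysis.

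Finally, the main stage depends on funding, and the interim hurdle is lenient and labelled as guidance. Both lower the urgency. Neither supplies the missing analysis.

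**Conclusion.** The mismatch of clocks is in the protocol, nothing in section 8.3 or the SAP allows for it, and it favours both drug arms on the question of improved ablation. Against that null, the final one-sided error per comparison is about 0.025 with no net delay and rises to 0.070 to 0.080 if the whole 12 weeks is extra. The figures assume exponential failure from FT, complete treatment, no dropout and events that all follow FT. Events that do not follow FT would reduce them. The control-arm wait decides where in the range the trial falls, and only data can supply it.

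Randomisation is a defensible primary origin and need not change. The plan should be amended before main-stage FFS data accrue, because it does not say which question it answers and has no analysis to separate a drug effect on ablation from the lead-in.

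**What to change.** In Protocol section 8.3, and in the main-stage SAP when written:

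1. Keep randomisation as the primary origin and keep all randomised men. State the estimand: the effect of the whole strategy on FFS from randomisation, or the effect of the drug on failure after FT.
2. Prespecify a required sensitivity analysis on a common assessment clock. Choose one: a grouped log-rank test or discrete-time Cox model by scheduled visit, or time from FT. Either needs a written rule for men who never have FT or who fail before it.
3. Report it beside the primary result at the 0.974 hurdle and at the final test. Do not attribute a benefit to improved ablation unless the two are consistent.
4. Report time from randomisation to FT by arm. The SAP already collects the dates, so the pilot can show the likely net delay.
5. Reconcile the clocks in sections 5.7 and 5.9: the PSA reference date against the FT-based visits, and the two ends of follow-up.

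The cost is wording, one extra model and an explicit rule for untreated men. Items 1 to 4 change no treatment, visit or sample size.
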